16.6 Appendix 6: Liver event and laboratory trigger definitions and follow-up requirements

Table 16-3 Liver Events and Laboratory Trigger Definitions

	Definition/ threshold
LIVER LABORATORY TRIGGERS	$3 \times \text{ULN} < \text{ALT} / \text{AST} \leq 5 \times \text{ULN}$ $1.5 \times \text{ULN} < \text{TBL} \leq 2 \times \text{ULN}$
LIVER EVENTS	ALT or AST $> 5 \times \text{ULN}$ ALP $> 2 \times \text{ULN}$ (in the absence of known bone pathology) TBL $> 2 \times \text{ULN}$ (in the absence of known Gilbert syndrome) ALT or AST $> 3 \times \text{ULN}$ and INR > 1.5

Potential Hy's Law cases (defined as ALT or AST > 3 × ULN and TBL > 2 × ULN [mainly conjugated fraction] without notable increase in ALP to > 2 × ULN)
Any clinical event of jaundice (or equivalent term)
ALT or AST > 3 × ULN accompanied by (general) malaise, fatigue, abdominal pain, nausea, or vomiting, or rash with eosinophilia
Any adverse event potentially indicative of a liver toxicity *

* These events cover the following: hepatic failure, fibrosis and cirrhosis, and other liver damage-related conditions; non-infectious hepatitis; benign, malignant and unspecified liver neoplasms
TBL: total bilirubin; ULN: upper limit of normal

Table 16-4 Follow up Requirements for Liver Events and Laboratory Triggers

Criteria	Actions required	Follow-up monitoring
Potential Hy's Law case ^a	Discontinue the study drug immediately Hospitalize, if clinically appropriate Establish causality Complete appropriate eCRF pages	ALT, AST, TBL, Alb, PT/INR, ALP and γGT until resolution ^c (frequency at investigator discretion)
ALT or AST > 8 × ULN	Discontinue the study drug immediately Hospitalize if clinically appropriate Establish causality Complete appropriate eCRF pages	ALT, AST, TBL, Alb, PT/INR, ALP and γGT until resolution ^c (frequency at investigator discretion)
> 3 × ULN and INR > 1.5	Discontinue the study drug immediately Hospitalize, if clinically appropriate Establish causality Complete appropriate eCRF pages	ALT, AST, TBL, Alb, PT/INR, ALP and γGT until resolution ^c (frequency at investigator discretion)
> 5 to ≤ 8 × ULN	Repeat LFT within 48 hours If elevation persists, continue follow-up monitoring If elevation persists for more than 2 weeks , discontinue the study drug Establish causality Complete appropriate eCRF pages	ALT, AST, TBL, Alb, PT/INR, ALP and γGT until resolution ^c (frequency at investigator discretion)

Criteria	Actions required	Follow-up monitoring
> 3 × ULN accompanied by symptoms ^b	Discontinue the study drug immediately Hospitalize if clinically appropriate Establish causality Complete appropriate eCRF pages	ALT, AST, TBL, Alb, PT/INR, ALP and γGT until resolution ^c (frequency at investigator discretion)
> 3 to ≤ 5 × ULN (patient is asymptomatic)	Repeat LFT within the next week If elevation is confirmed, initiate close observation of the patient	Investigator discretion Monitor LFT within 1 to 4 weeks
ALP (isolated)		
> 2 × ULN (in the absence of known bone pathology)	Repeat LFT within 48 hours If elevation persists, establish causality Complete appropriate eCRF pages	Investigator discretion Monitor LFT within 1 to 4 weeks or at next visit
TBL (isolated)		
> 2 × ULN (in the absence of known Gilbert syndrome)	Repeat LFT within 48 hours If elevation persists, discontinue the study drug immediately Hospitalize if clinically appropriate Establish causality Complete appropriate eCRF pages	ALT, AST, TBL, Alb, PT/INR, ALP and γGT until resolution ^c (frequency at investigator discretion) Test for hemolysis (e.g., reticulocytes, haptoglobin, unconjugated [indirect] bilirubin)
> 1.5 to ≤ 2 × ULN (patient is asymptomatic)	Repeat LFT within the next week If elevation is confirmed, initiate close observation of the patient	Investigator discretion Monitor LFT within 1 to 4 weeks or at next visit
Jaundice	Discontinue the study drug immediately Hospitalize the patient Establish causality Complete appropriate eCRF pages	ALT, AST, TBL, Alb, PT/INR, ALP and γGT until resolution ^c (frequency at investigator discretion)
Any AE potentially indicative of a liver toxicity*	Consider study drug interruption or discontinuation Hospitalization if clinically appropriate Establish causality Complete appropriate eCRF pages	Investigator discretion

* These events cover the following: hepatic failure, fibrosis and cirrhosis, and other liver damage-related conditions; non-infectious hepatitis; benign, malignant and unspecified liver neoplasms

Criteria	Actions required	Follow-up monitoring
-----------------	-------------------------	-----------------------------

TBL: total bilirubin; ULN: upper limit of normal

^a Elevated ALT/AST > 3 × ULN and TBL > 2 × ULN but without notable increase in ALP to > 2 × ULN

^b (General) malaise, fatigue, abdominal pain, nausea, or vomiting, or rash with eosinophilia

^c Resolution is defined as an outcome of one of the following: (1) return to baseline values, (2) stable values at three subsequent monitoring visits at least 2 weeks apart, (3) remain at elevated level after a maximum of 6 months, (4) liver transplantation, and (5) death.

NSAID	Non-Steroidal Anti-Inflammatory Drug	
PCS	Physical Component Summary	
PD	Pharmacodynamic(s)	
PK	Pharmacokinetic(s)	
PRN	as needed	
PRO	Patient Reported Outcome	
PSQI	Pittsburgh Sleep Quality Index	
PT	Preferred term	
q4w	Every 4 weeks	
QoL	Quality of Life	
RMP	Risk Management Plan	
SAE	Serious Adverse Event	
SD	Standard Deviation	
SF-36	Medical Outcome Short Form (36) Health Survey	
SF-36 PCS	Short Form-36 Physical Component Summary	
SOC	System Organ Class	
SMQ	Standardized MedDRA Query	
SpA	Spondyloarthritis	
TBL	Total Bilirubin	
TNF-IR	TNFα Inhibitor Incomplete Responder	
TNF/TNFα	Tumor Necrosis Factor	
ULN	Upper Limit of Normal	
VAS	Visual Analog Scale	
VS	Versus	

1 Introduction

Data will be analyzed by Novartis according to the data analysis Section 12 of the clinical study protocol. The statistical methodology is described below and any deviations from the protocol are documented. Additional detailed information regarding the analysis methodology is contained in the Appendix section.

1.1 Study design

This multicenter study uses a randomized, double-blind, placebo-controlled, parallelgroup design to study the efficacy, safety, and tolerability of treatment with intravenous secukinumab (initial dose of 6 mg/kg followed thereafter with 3 mg/kg administered every four weeks starting at Week 4) in subjects with active axSpA. The study population consists of approximately 400 subjects with active AS and approximately 100 subjects with active nraxSpA, despite current or previous NSAID, conventional DMARD and / or TNF inhibitor therapy, or intolerance to these therapies. A screening (SCR) period of up to 10 weeks will be used to assess eligibility, followed by randomization to 52 weeks of study treatment.

At baseline, subjects with active AS and nr-axSpA will be randomized to one of the two treatment groups:

- Group 1: approximately 200 AS subjects and approximately 50 nr-axSpA subjects; These subjects will receive secukinumab 6 mg/kg i.v. at randomization (Baseline (BSL) visit), followed by the administration of secukinumab 3 mg/kg i.v. every four weeks starting at Week 4 through Week 48 (exposure through Week 52).
- Group 2: approximately 200 AS subjects and approximately 50 nr-axSpA subjects; These subjects will receive i.v. placebo at randomization (BSL visit), Weeks 4, 8, and 12, followed by the administration of secukinumab 3 mg/kg i.v. at Week 16 and every four weeks through Week 48 (exposure through Week 52).

This study will consist of 4 periods totaling 70 weeks: the screening period (up to 10 weeks), the treatment period 1 (total duration of 16 weeks) and the treatment period 2 (total duration of 36 weeks) followed by the safety follow up period of 8 weeks after the end of treatment visit (i.e., Week 52).

The subjects will be stratified at randomization according to disease condition (i.e., AS or nr-axSpA). No more than 20% TNF Inhibitor Incomplete Responders (TNF-IR) subjects will be enrolled in the study. Starting at Week 16, all subjects will switch to open-label intravenous secukinumab, including all placebo subjects.

No subject will be on placebo treatment after Week 16, because axSpA is considered a chronic disease with no 'true' and lasting placebo response. However, all subjects and investigators/site staff will remain blinded to the original randomized treatment group assignment (secukinumab treatment vs placebo). Study treatment will continue up to Week 52. An end of treatment visit (i.e., Week 52) is to be done 4 weeks after last study treatment administration and a post treatment follow-up visit (i.e., Week 60) is to be done 8 weeks after the end of treatment visit for all subjects (regardless of whether they complete the entire study as planned or discontinue prematurely). All i.v. infusions will be performed at the study site and site personnel will administer the infusions to subjects.

Novartis	Confidential	Page 9 of 45
SAP		Study No. CAIN457P12301

Rescue medication is not allowed until Week 16. However, subjects who are deemed by the investigator not to be benefiting from the study treatment based on safety and efficacy assessments or for any reason of their own accord will be free to discontinue participation in the study at any time. The study will have a primary endpoint analysis at Week 16. Therefore, the primary analysis will be performed with Week 16 data once the last subject has completed the Treatment Period 1.

The primary endpoint analysis will be performed after all subjects complete Week 16 in order to support regulatory filing. As the primary analysis is scheduled at Week 16, no adjustment will be made to the testing strategy to control family-wise type I error rate for this analysis.

1.2 Study objectives and endpoints

1.2.1 Primary objective

The primary objective is to demonstrate that the efficacy of i.v. secukinumab at Week 16 is superior to placebo in subjects with active axSpA (AS and nr-axSpA) based on the proportion of subjects achieving an ASAS40 (Assessment of SpondyloArthritis International Society criteria) response.

1.2.2 Secondary objectives

- 1. To demonstrate that the efficacy of i.v. secukinumab at Week 16 is superior to placebo based on the proportion of subjects achieving Ankylosing Spondylitis Disease Activity Score (ASDAS)-C-Reactive Protein (CRP) major improvement
- 2. To demonstrate that the efficacy of i.v. secukinumab at Week 16 is superior to placebo based on the change from baseline in total Bath Ankylosing Spondylitis Disease Activity Index (BASDAI)
- 3. To demonstrate that the efficacy of i.v. secukinumab at Week 16 is superior to placebo based on the proportion of subjects meeting the ASAS 5/6 response criteria
- 4. To demonstrate that the efficacy of i.v. secukinumab at Week 16 is superior to placebo based on the change from baseline of Bath Ankylosing Spondylitis Functional Index (BASFI)
- 5. To demonstrate that the efficacy of i.v. secukinumab at Week 16 is superior to placebo based on the change from baseline in Short Form-36 Physical Component Summary (SF-36 PCS)
- 6. To demonstrate that the efficacy of i.v. secukinumab at Week 16 is superior to placebo based on the change from baseline in Ankylosing Spondylitis Quality of Life (ASQoL) scores
- 7. To demonstrate that the efficacy of i.v. secukinumab at Week 16 is superior to placebo based on the change from baseline in high sensitivity C-Reactive Protein (hsCRP)
- 8. To demonstrate that the efficacy of i.v. secukinumab at Week 16 is superior to placebo based on the proportion of subjects achieving an ASAS20 response
- 9. To demonstrate that the efficacy of i.v. secukinumab at Week 16 is superior to placebo based on the proportion of subjects achieving Ankylosing Spondylitis Disease Activity Score (ASDAS)-C-Reactive Protein (CRP) inactive disease
- 10. To demonstrate that the efficacy of i.v. secukinumab at Week 16 is superior to placebo based on the proportion of subjects achieving ASAS partial remission

Novartis	Confidential	Page 10 of 45
SAP		Study No. CAIN457P12301

- 11. To demonstrate that the efficacy of i.v. secukinumab at Week 16 is superior to placebo based on the change from baseline in Pittsburgh Sleep Quality Index (PSQI)
- 12. Overall safety and tolerability of i.v. secukinumab compared to placebo as assessed by physical exams, vital signs, laboratory assessments and adverse event monitoring

2 Statistical methods

2.1 Data analysis general information

To support the submission, tables and figures will be generated for overall axSpA population. Listings will be generated for overall axSpA population and will be sorted by disease condition (AS and nr-axSpA), except for the listing of randomization allocation to treatment which will be sorted by the randomization number.

Summary statistics for continuous variables will include N, mean, standard deviation, minimum, lower quartile, median, upper quartile and maximum. Summary statistics for discrete variables will be presented in the number and percent of subjects in each category.

Data analyses will be presented by treatment regimen. Efficacy and safety data for the placebocontrolled period (or the entire treatment period as appropriate) will be presented by the following 2 treatment groups. Subjects may be included in more than one treatment group for some analyses (e.g., exposure-adjusted adverse events over the entire treatment period). The 2 treatment groups represent the regimens subjects will be eligible to be randomized to for the first 16 weeks of the study.

- Secukinumab regimen: approximately 200 AS subjects and approximately 50 nr-axSpA subjects; These subjects will receive secukinumab 6 mg/kg i.v. at randomization (Baseline (BSL) visit), followed by the administration of secukinumab 3 mg/kg i.v. every four weeks starting at Week 4 through Week 48 (exposure through Week 52).
- Placebo regimen: approximately 200 AS subjects and approximately 50 nr-axSpA subjects; These subjects will receive i.v. placebo at randomization (BSL visit), Weeks 4, 8, and 12, followed by the administration of secukinumab 3 mg/kg i.v. at Week 16 and every four weeks through Week 48 (exposure through Week 52).

Note that the treatment groups above for a subject may differ depending on the time period of the analysis and whether one assesses the subject for efficacy or safety.

Comparative efficacy data

Comparative efficacy analyses (i.e., inferential efficacy comparisons with placebo) will focus on the time period when both active drug and the placebo are given in a manner suitable for making comparisons (e.g., double-blind). For AIN457P12301, this is the first 16-weeks of treatment. Comparative efficacy will be performed based on the Full Analysis Set (FAS) population using the randomized treatment. Data collected after Week 16 will generally be summarized descriptively on the FAS population using treatment sequence.

Efficacy data following treatment switch

Data will also be presented after Week 16, by a combination of the 'original' and 'switch' treatment groups and will be referred to as treatment sequence. These treatment sequences represent the treatment combinations the subjects experience over the course of the entire trial

Novartis	Confidential	Page 12 of 45
SAP		Study No. CAIN457P12301

in case of switch (e.g., placebo patients who are reassigned to secukinumab 3 mg/kg i.v. at Week 16).

All listings will be presented by treatment sequence.

2.2 Analysis sets

The following analysis sets will be used in this trial:

Randomized set: The randomized set will be defined as all subjects who were randomized. Unless otherwise specified, mis-randomized subjects (mis-randomized in IRT) will be excluded from the randomized set.

Mis-randomized subjects are defined as those subjects who were mistakenly randomized into the IRT prior to the site confirming all eligibility criteria had been met and to whom no study medication was given. Mis-randomized patients are treated as screen failures.

Full analysis set (FAS): The FAS will be comprised of all subjects from the randomized set to whom study treatment has been assigned. Following the intent-to-treat principle, subjects will be evaluated according to the treatment assigned to at randomization, but actual stratum, if stratified randomization is used.

Safety set: The safety set includes all subjects who took at least one dose of study treatment during the treatment period. Subjects will be evaluated according to treatment received.

2.2.1 Treatment groups

The summaries by treatment will primarily be performed by the randomized treatment but also by combination of randomized treatment and switch treatment. For some safety summaries (e.g., exposure-adjusted) the 'switch' treatment may be summarized separately.

- Randomized treatment:
 - AIN457 6 mg/kg 3 mg/kg i.v.
 - Placebo
- Treatment sequence:
 - AIN457 6 mg/kg 3 mg/kg i.v.
 - Placebo AIN457 3 mg/kg i.v.
 - Placebo Not Switch
- Switch treatments (for placebo patients who cross-over):
 - AIN457 3 mg/kg i.v. (will only be counted under Any AIN457)

2.2.2 Subgroup of interest

The primary and secondary endpoints will be analyzed by disease condition (AS and nr-axSpA). Analyses by previous use of TNF- α inhibitor may also be provided for overall axSpA population.

Novartis	Confidential	Page 13 of 45
SAP		Study No. CAIN457P12301

2.3 Patient disposition, demographics and other baseline characteristics

2.3.1 Patient disposition

The number of subjects screened will be presented. In addition, the reasons for screen failures will be provided. The number and percentage of subjects in the randomized set who completed the study periods and who discontinued the study prematurely (including the reason for discontinuation) will be presented at the end of each treatment period (Week 16 and Week 52) and follow-up period, if appropriate, for each treatment group and all subjects.

For each protocol deviation (PD), the number and percentage of subjects for whom the PD applies will be tabulated. Protocol deviations due to COVID-19 will be reported in separate categories.

Additional analysis due to COVID-19 might be provided, e.g., summary of participants missed visit and/or treatment due to COVID-19.

2.3.2 Background and demographic characteristics

Data on background and demographic characteristics have been summarized in the Week 16 Clincial Study Report (CSR) and will not be reproduced for the Final Analysis.

2.3.3 Medical history

Data on medical history and smoking history have been summarized in Week 16 CSR and will not be reproduced for the Final Analysis.

2.4 Treatments (study treatment, rescue medication, concomitant therapies, compliance)

2.4.1 Study treatment / compliance

The analysis of study treatment data will be based on the safety set. The number of active and placebo i.v. infusions received will be presented by treatment group. The duration of exposure to study treatment will also be summarized by treatment group. In addition, the number and percentage of subjects with cumulative exposure levels (e.g., any exposure, ≥ 4 weeks, ≥ 8 weeks, etc.) will be presented.

Duration of exposure will be defined as the time from first dose of study treatment to the time of treatment switch (for subjects who switch from placebo to open-label secukinumab) or minimum of (last dose of the treatment + 84 days) and (last visit date). Patients who switch treatment during the study (e.g., from placebo to open-label secukinumab treatment at Week 16) will have exposure to both medications using the appropriate start and stop dates.

Duration of exposure (years) = duration of exposure (days) / 365.25

Duration of exposure (100 subject years) = duration of exposure (years) / 100

The analyses of duration of exposure described above will be done for the entire study treatment period.

Novartis	Confidential	Page 14 of 45
SAP		Study No. CAIN457P12301

2.4.2 **Prior**, concomitant and post therapies

Prior medications have been summarized in the Week 16 CSR and will not be reproduced for the Final Analysis.

Any medication given at least once between the day of first dose of randomized study treatment and within 84 days after last dose will be a concomitant medication, including those which were started pre-baseline and continued into the period where study treatment is administered.

Concomitant medications will be presented in alphabetical order, by Anatomical Therapeutic Classification (ATC) codes and grouped by anatomical main group (the 1st level of the ATC codes). Tables will show the overall number and percentage of subjects receiving at least one treatment of a particular ATC code and at least one treatment in a particular anatomical main group.

Significant concomitant non-drug therapies and procedures will be summarized by primary system organ class and MedDRA preferred term.

Any non-drug therapies and procedures done between the day of first dose of study treatment and within 84 days after last dose will be defined as concomitant non-drug therapies and procedures, including those which were started pre-baseline and continued into the period where study treatment is administered.

The number and percentage of subjects receiving concomitant axSpA therapy will be presented by randomized treatment group and the total duration of previous exposure to axSpA therapies.

Prior or concomitant medications will be identified by comparing recorded or imputed start and end dates of medication taken to the reference start date.

2.5 Analysis of the primary objective

The primary efficacy variable is response to treatment according to the ASAS40 criteria at Week 16 in patients with active axSpA (AS and nr-axSpA).

The analysis of primary variable at Week 16 will not be reproduced for the Final Analysis.

2.6 Analysis of secondary objectives

The secondary efficacy variables include,

- response to treatment at Week 16 according to the ASDAS-CRP major improvement criteria
- change from baseline in BASDAI at Week 16
- response to treatment at Week 16 according to the ASAS 5/6 criteria
- change from baseline in total BASFI score at Week 16
- change from baseline in SF-36 PCS at Week 16
- change from baseline in ASQoL at Week 16
- change from baseline in hsCRP at Week 16
- response to treatment at Week 16 according to the ASAS20 criteria

Novartis	Confidential	Page 15 of 45
SAP		Study No. CAIN457P12301

- response to treatment at Week 16 according to the ASDAS-CRP inactive disease criteria
- response to treatment at Week 16 according to the ASAS partial remission
- change from baseline in PSQI at Week 16

The analysis of secondary variables at Week 16 will not be reproduced for the Final Analysis.

2.8 Safety analyses

Summaries may performed separately for the entire treatment period. The analyses of the follow-up period will be limited to summaries for treatment-emergent adverse events, serious adverse events and risks based on adverse events.

Safety analyses will be performed on treatment received or actual treatment as described below:

Novartis	Confidential	Page 17 of 45
SAP		Study No. CAIN457P12301

The actual treatment or treatment received for summaries of safety data will differ to the treatment assigned at randomization only if a subject received the wrong treatment during the entire study.

For those subjects who received not the treatment randomized, i.e., who received erroneously the wrong treatment at least once, an additional AE listing will be prepared displaying which events occurred after the treatment errors.

In addition for subjects who discontinue study treatment but continue with study participation, an additional AE listing will be prepared displaying which events occurred after the study treatment discontinuation.

2.8.1 Adverse events (AEs)

The crude incidence of treatment emergent adverse events (i.e., events started after the first dose of study treatment or events present prior to the first dose of study treatment but increased in severity based on preferred term and on or before last dose date + 84 days) will be summarized by primary system organ class and preferred term. Confidence intervals for the crude rate will be derived as described in Section 5.4.3. In addition, exposure time-adjusted incidence rates including 95% confidence intervals will be provided for the entire treatment period (see Section 5.4.4). A graphical display of the crude incidence rates and exposure-adjusted rates will be presented for all AEs and serious AEs by system organ class.

Adverse events reported will be presented in descending frequency according to its incidence in the secukinumab group starting from the most common event. Summaries (crude incidences only) will also be presented for AEs by severity and for study treatment related AEs. If a particular AE 'severity' is missing, this variable will be listed as missing and treated as missing in summaries. If a subject reported more than one adverse event with the same preferred term, the adverse event with the greatest severity will be presented. If a subject reported more than one adverse event within the same primary system organ class, the subject will be counted only once with the greatest severity at the system organ class level, where applicable.

Separate summaries will be provided for adverse events suspected to be related to study drug, deaths, serious adverse events, and adverse events leading to discontinuation and adverse events requiring concomitant medication.

Adverse events will also be reported separately by Standardized MedDRA Query (SMQ) according to MedDRA, using a narrow search. The MedDRA version used for reporting the study will be described in a footnote.

A listing of non-treatment emergent adverse events will be provided. These adverse events occurred before the first dose of the study treatment. The crude incidence rate will be provided without treatment information.

For SAEs occurred during screening a listing will be prepared for all subjects screened including screening failures.

An overview of the safety analyses which will be performed for treatment emergent AEs, labs and vital signs for each analysis period is described in Table 2-1.

	Overview	w of allalyse	5 011 50111e 5d	nety enupon	113	
Analysis period	AEs & SAEs	AEs by severity	Study drug related AEs	AEs-SMQ	Risk	Notables for (vitals), lab criteria
Day 1 – Week 16	 crude incidence 	 crude incidence 	 crude incidence 	• crude incidence	 crude incidence 	• crude incidence
Entire Treatment	 crude incidence exposure time adjusted incidence 	• crude incidence	• crude incidence	• exposure time adjusted incidence	 crude incidence exposure time adjusted incidence 	• crude incidence

	Table 2-1	Overview of anal	yses on some	safety endpoints
--	-----------	-------------------------	--------------	------------------

Exposure-adjusted incidence rates will be done for the following:

• Primary SOC level for AE and SAE

• Level 1 for Risks and SMQ analyses

• PT level for AE and SAE

Algorithms for date imputations will be provided in Programming Datasets Specifications.

For the legal requirements of ClinicalTrials.gov and EudraCT, two required tables on **on-treatment/treatment emergent** adverse events which are not serious adverse events with an incidence greater than x% and on **on-treatment/treatment emergent** serious adverse events and SAE suspected to be related to study treatment will be provided by system organ class and preferred term on the safety set population. Here threshold value x is set to 2 (%), but it may be updated following review of the dry run outputs.

If for a same patient, several consecutive AEs (irrespective of study treatment causality, seriousness and severity) occurred with the same SOC and PT:

- a single occurrence will be counted if there is ≤ 1 day gap between the end date of the preceding AE and the start date of the consecutive AE
- more than one occurrence will be counted if there is > 1 day gap between the end date of the preceding AE and the start date of the consecutive AE

For occurrence, the presence of at least one SAE/SAE suspected to be related to study treatment/non SAE has to be checked in a block e.g., among AEs in $a \le 1$ day gap block, if at least one SAE is occurring, then one occurrence is calculated for that SAE.

The number of deaths resulting from SAEs suspected to be related to study treatment and SAEs irrespective of study treatment relationship will be provided by SOC and PT.

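### Over the entire treatment period, AEs by severity, study-drug-related AEs and notable lab/vital values get crude incidence only, although follow-up per treatment is unequal by design

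*SAP*

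**What the plan says.** SAP 2.8.1 plans, for overall adverse events, that "exposure time-adjusted incidence rates including 95% confidence intervals will be provided for the entire treatment period". For two breakdowns of the same events it stops short of that: "Summaries (crude incidences only) will also be presented for AEs by severity and for study treatment related AEs".

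Table 2-1 in the same section has two rows.

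- **Day 1 to Week 16:** crude incidence in every column.
- **Entire Treatment:** crude and exposure-adjusted incidence for AEs & SAEs and for Risk, and exposure-adjusted incidence for SMQs. The columns for AEs by severity, study drug related AEs and "Notables for (vitals), lab criteria" show crude incidence only.

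The list under the table that begins "Exposure-adjusted incidence rates will be done for the following" names AEs and SAEs (SOC and PT level) and risks and SMQs (level 1). It does not name severity, relatedness or notable values.

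On follow-up, SAP 2.4.1 states: "Duration of exposure will be defined as the time from first dose of study treatment to the time of treatment switch". That end applies to subjects who switch from placebo. Otherwise exposure ends at the earlier of 84 days after the last dose and the last visit. SAP 2.2.1 lists the switch treatment of placebo subjects as "AIN457 3 mg/kg i.v. (will only be counted under Any AIN457".

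Protocol 12.5.2 asks for exposure-adjusted AE incidence where appropriate and does not say for which summaries.

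**The concern.** A crude incidence is the share of subjects with at least one event, so it grows with time at risk. Here time at risk differs between treatments by design: placebo stops at Week 16 and secukinumab continues. Set side by side over the entire period, crude percentages mix any treatment effect with length of follow-up. A reader could see a several-fold excess of severe or related events on secukinumab where the rates are the same, and could not separate a real difference from the extra time.

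The SAP already handles this for AEs/SAEs, SMQs and risks, and gives no reason for treating the other three categories differently. Safety compared with placebo, including AEs, laboratory values and vital signs, is a stated secondary objective (SAP 1.2.2, item 12). The entire-period tables are also the ones that carry the safety data collected after Week 16.

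**Working it through.** **1. Timeline.** SAP 1.1 says: "This study will consist of 4 periods totaling 70 weeks". It gives up to 10 weeks of screening, then "the treatment period 1 (total duration of 16 weeks) and the treatment period 2 (total duration of 36 weeks"), then 8 weeks of follow-up. 10 + 16 + 36 + 8 = 70 weeks, which reproduces the stated total.

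**2. Time per treatment for a completer.**
- Placebo, ending at the switch: 16 weeks.
- Randomized secukinumab: 16 + 36 = 52 weeks of treatment. The last dose is at Week 48 (day 336), and 336 + 84 = 420 days = Week 60. The range is therefore 52 to 60 weeks.
- Placebo subjects after the switch, under Any AIN457: 52 − 16 = 36 to 60 − 16 = 44 weeks.
- Ratio of randomized secukinumab to placebo time: 52/16 = 3.25 to 60/16 = 3.75.

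**3. Crude incidence under equal rates.** SAP 5.4.4 models first occurrences as approximately a Poisson process with constant intensity. On that model, crude incidence = 1 − exp(−rate × weeks/52.18). The documents give no event rates. The rates below are an assumption, the same in both arms, so the true rate ratio is 1.0 in every line.

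| Rate per patient-year | Placebo, 16 wk | Secukinumab, 52 wk | Secukinumab, 60 wk | Ratio 52/16 | Ratio 60/16 |
|---|---|---|---|---|---|
| 0.05 | 1.5% | 4.9% | 5.6% | 3.19 | 3.67 |
| 0.1 | 3.0% | 9.5% | 10.9% | 3.14 | 3.60 |
| 0.2 | 5.9% | 18.1% | 20.5% | 3.04 | 3.45 |
| 0.5 | 14.2% | 39.2% | 43.7% | 2.76 | 3.08 |
| 1.0 | 26.4% | 63.1% | 68.3% | 2.39 | 2.59 |
| 2.0 | 45.8% | 86.4% | 90.0% | 1.88 | 1.96 |

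For example, at 1.0 per year over 16 weeks: 1 − exp(−1.0 × 16/52.18) = 26.4%.

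**4. Pooled Any AIN457.** With 1:1 allocation, half the subjects contribute 60 weeks and half 44. Averaging the two incidences and dividing by the 16-week placebo value gives 3.19 at 0.05 per year, falling to 1.87 at 2.0 per year. If time stops at Week 52 (52 and 36 weeks), the same steps give 2.71 falling to 1.76.

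**5. Other possible columns.** SAP 2.2.1 says summaries are primarily by randomized treatment, and also by treatment sequence. Under either, a placebo subject's post-switch events can stay with the placebo group or the placebo-to-secukinumab sequence. Follow-up is then similar for completers and the ratios above do not arise, but the column contains events on two treatments.

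**6. Notable values.** These are found only when a measurement is taken. In SAP Table 5-4, hematology and chemistry have four post-baseline windows through Week 16 (Weeks 4, 8, 12, 16) and nine through Week 60 (adding Weeks 24, 32, 40, 52, 60). Longer follow-up therefore also means more chances of detection.

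**The case against.** The strongest reply is that a valid comparison is already planned. The Day 1 to Week 16 row covers all three categories over equal planned time. This stands, and it limits the point to the entire-period tables. It does not make those tables readable, and it says nothing about severe or related event rates after Week 16.

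Second, the 16-week placebo column is an inference. It rests on SAP 2.2.1, 2.4.1 and 5.4.4, and no section states the columns of the crude entire-period tables. This also stands. A reader might infer that the SAP has committed itself to setting 16 weeks of placebo against 52 to 60 weeks of secukinumab; the text does not go that far. The alternative layouts mix treatments, so the columns need stating in any case.

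Third, the tables are descriptive, the main entire-period outputs are adjusted, duration of exposure is reported by group, and the protocol leaves exposure adjustment to judgement. All true: this is not a departure from the protocol. Percentages shown by treatment group will still be compared.

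Fourth, a person-time rate suits notable values poorly. Some, such as a low pulse or low diastolic pressure, may reflect a stable trait seen early. With a front-loaded hazard, a constant-intensity rate would dilute the arm followed longer. This stands and changes the remedy for that category. It is also unsettled how far notable values run: SAP 2.8 limits follow-up-period analyses to AEs, SAEs and AE-based risks, while SAP 2.8.2 and 2.8.3.1 include data up to 84 days after the last dose.

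**Conclusion.** The point holds for the entire-period tables only. Three categories are left as crude incidence in a row where the SAP adjusts the others for exposure. If the columns follow the SAP's exposure definition, equal true rates would appear as a crude ratio of about 1.9 to 3.7 for randomized secukinumab, and about 1.9 to 3.2 for pooled Any AIN457 followed to Week 60. These sizes assume completers, a constant rate equal in both arms, and 0.05 to 2.0 events per patient-year; the rates are not from the documents. If the columns follow randomized treatment or sequence instead, the fault is a placebo column that mixes treatments.

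A reader might infer that severe events, related events or notable values cannot be compared with placebo at all in this trial. The documents do not support that, because the Week 16 tables allow the comparison. No efficacy conclusion is affected. It is a worthwhile, inexpensive correction to safety reporting.

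**What to change.** 1. In the Entire Treatment row of Table 2-1, and in the list of exposure-adjusted outputs below it, add exposure-adjusted incidence rates for severe AEs and study-drug-related AEs. Use the method and confidence interval of SAP 5.4.4, with events and time attributed to the treatment at onset, as its worked example for a switching subject already does. Amend the crude-only sentence in SAP 2.8.1 to match.
2. For notable laboratory and vital sign values, omit the placebo column from the entire-period crude table and refer readers to the Day 1 to Week 16 table for the placebo comparison.
3. State the columns of every entire-period crude table: treatment at onset, randomized treatment or treatment sequence.

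The cost is a few extra descriptive tables using a method the SAP already specifies. Sample size, type I error and trial conduct are unchanged.
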